1.4 Preliminary Data

Effects of MORE on cognitive, affective, and psychophysiological mechanisms implicated in addiction.

[name] conducted the first pilot randomized controlled trial (RCT; N=53) of MORE, and found that, relative to a support group (SG) control, MORE significantly decreased stress, modified addiction attentional bias, and increased heart rate variability recovery from substance cues during an affect-modulated cue-reactivity protocol. Two follow-up studies (N=58) found that trait mindfulness among substance dependent individuals in treatment was negatively associated with addiction attentional bias and positively associated with heart rate variability recovery from stress-primed cue-exposure.^{8,9}

MORE as a treatment for opioid misuse and chronic pain – preliminary outcomes and processes.

[name] recently completed a pilot RCT of 8 sessions of MORE for chronic pain patients receiving long-term opioid analgesic therapy. In the course of 1.5 years, 304 patients were recruited from community sources, 115 of whom met study criteria and were randomly assigned to treatment. Eighty-one percent of participants who began the study treatments completed treatment and were retained at the post-treatment assessment. Intent-to-treat analyses indicate that compared with a support group (SG; n=58) control, MORE (n=57) led to significant reductions in pain severity (p=.014, d=.63) and functional interference (p=.002; d=.84) that were maintained at 3-month follow-up and mediated by non-reactivity and reinterpretation of pain as innocuous sensory signals. Importantly, MORE improved addiction-related outcomes. Relative to SG, a greater proportion of opioid misusers treated with MORE no longer exceeded the validated threshold for opioid misuse following treatment, due to reductions in aberrant drug-related behavior, X^2 =3.74, p=.05. MORE also significantly reduced opioid craving by post-treatment (p=.027, d=.50), and significantly decreased the correlation strength between craving and misuse.

MORE and ecological momentary assessment of pain and affect.

In a sample of low SES individuals with OUD and comorbid psychiatric disorders, MORE (n=20) led to significantly greater reductions in opioid craving (p=.04, d=.63) and PTSD symptoms (p=.001, d=.84) compared to Cognitive Behavioral Therapy (CBT).¹⁰. In this trial, across 8 weeks of treatment, patients completed up to 224 EMA measures of pain and affect. Multilevel models and generalized estimating equations examined effects of treatment on momentary pain and positive affect, and generalized linear models examined associations between pain and affect

6

Version Number: 15, 2/2/2022 Protocol Number: Pro20190016877

PI Name: [name]

Protocol Title: Mindfulness Oriented Recovery Enhancement (MORE) as an Adjunct to Methadone Treatment RESERVED FOR IRB STAMP
DO NOT MODIFY THIS SPACE

and changes in opioid misuse by post-treatment. Patients in MORE reported significantly greater improvements in momentary pain (p=.01) and positive affect (p=.004) than patients in the SG. Further, over the entire course of treatment, patients in MORE were significantly more likely to exhibit positive affect regulation (OR=2.75) than patients in the SG. Finally, improvements in positive affect (but not pain) over the course of intervention were associated with reduced risk of misusing opioids by post-treatment (p=.02).

1.5 Sample Size Justification

With 1.5 years of subject accrual and an additional follow-up of 16 weeks after the accrual interval, our study needs 47 subjects per group to test a hazard ratio of 0.55 when comparing MORE to TAU, with 80% power and alpha=5% (two-sided). To account for attrition, we will recruit up to 92 subjects per group (a total of 184 subjects at a 1:1 ratio for MORE vs. TAU).

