in-person. Participants will be asked to sign the electronic consent form on Qualtrics or REDCap, mail a signed paper version back to the research assistant, or drop off a signed paper version to their clinic for research staff to pick up. Alternatively, consenting maybe be done in-person. Participants will also keep a copy of the consent for their records.

Participants randomized to the MORE condition will participate in eight, weekly, two-hour online group sessions led by a clinic or study counselor. Each session will contain 5 to 9 participants and will be conducted online through secure video or phone conferencing. If a participant is unable to join the MORE session through video conference due to technical difficulties at the time of the session, the participant will be instructed to join the session by phone or the participant may go to their clinic and a research or clinic staff member can help them access the intervention through their tablet or a computer. Attendance at each session and reasons for missing sessions will be recorded. Participants randomized to the control condition will continue receiving treatment as usual at their clinic.

All study participants will partake in a total of three interviews lasting up to 120 minutes occurring at baseline, 8-, and 16-weeks (week 1 will be considered the week of the first MORE group session) by video or phone conferencing or in-person. If more than 3 months since baseline survey was administered from start of group (study intervention), clients will be asked to do another baseline survey. Each participant will also have a urine or saliva sample collected during each assessment. This is required to verify self-report of drug use. Due to social desirability, it is common for people to not accurately report drug use; therefore, biochemical verification is the gold standard measure of drug use. Participants will be mailed a urine or saliva test prior to the interview.

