All study participants will participate in three video, phone conferencing, or in-person visits at baseline, 8-, and 16-weeks. Information will be collected on demographic characteristics, substance use, methadone treatment, opioid craving and withdrawal, physical pain, non-reactivity, negative and positive affect, attentional bias, cognitive and

Version Number: 15, 2/2/2022 Protocol Number: Pro20190016877 PI Name: [name]

Protocol Title: Mindfulness Oriented Recovery Enhancement (MORE) as an Adjunct to Methadone Treatment RESERVED FOR IRB STAMP
DO NOT MODIFY THIS SPACE

mental health, physical health, and intervention implementation and attitudes. At the baseline and 8-week research visits, participants will complete three cognitive tasks on a computer or tablet that assess inhibitory control, implicit (automatic) associations, and the precedence of global features in visual perception. Urine and/or saliva samples will be requested at each assessment for confirmation of self-reported drug use or recent drug test results will be obtained from the participants' clinic chart. In addition, participants will partake in daily ecological momentary assessments (EMA) throughout the 16-weeks of study participation that include brief measures of pain intensity, mood, and substance use. Participants will also be asked to initiate communication via smartphone, computer, or tablet when they either lapse to opioid use or experience serious craving. Self-initiated responses will include information about the circumstances surrounding their craving/lapse. A synopsis of all study instruments are included below (see 1.98 – Study instruments).

C. Define the duration of the study and the length of time each subject will participate in the study. This study is expected to take two years. Each subject will participate in the study for a total of 16-weeks.

- **D.** Describe any primary and secondary study or safety endpoints
 - Primary Outcome: time until opioid relapse
 - Secondary Outcomes: opioid abstinence, days of drug use, MMT adherence, craving, pain symptoms, and emotional distress

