Hypothesis 1.1. (**Primary Outcome**) MORE will result in longer duration of time to first opioid lapse and MMT dropout than TAU. We will use survival analysis (Kaplan Meier curves and marginal model analysis for multivariate survival data)³⁴ to test effects of MORE vs. TAU on time until first opioid lapse and MMT dropout—evidenced either on EMA, Timeline Follow-Back, urinalysis or medical records (whichever is first). Survival analysis will be run once, at 16 weeks post-baseline. Clustering within cohort will be adjusted in the multivariate marginal model analysis.³⁴ We will estimate the hazard ratios of opioid lapse and MMT dropout when comparing MORE with TAU, controlling for covariates.

Hypotheses 1.2 and 1.3 (Secondary Outcomes). MORE will result in more days of opioid abstinence (or less days of use) and a higher rate of biochemically-verified abstinence over time than TAU. Generalized linear mixed model (GLMM)³⁵ repeated measures analysis will be used. Specifically, identity link will be used for "number of abstinent days" as the dependent variable, and logit link will be used for "opioid abstinence (yes/no via urinalysis)" as the dependent variable. Days of use/abstinence will be assessed via EMA, number of drug use days since last visit and past 30 days, and the Timeline Follow-Back. In cases of conflicting findings across data sources, we will assume the highest number of days of use or lowest number of abstinent days recorded for that period. Analyses will include group (MORE vs. TAU), time, and group by time interactions as the fixed effects independent variables. Correlations among repeated measures and among subjects within cohorts will be modeled using nested random effects. Potential confounders that meet the p<0.10 criterion stated above will be entered as covariates. Linear contrasts will be constructed to test between-group differences in "days of use" or "days of abstinence" separately at each timepoint. In comparing days of use, if a substantial proportion of subjects do not use opioids, resulting in excessive zero days of use, we will use a two-part logistic/linear analysis model.^{36,37}

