C11. Outcomes and Future Directions. We expect to establish the efficacy of an innovative intervention that can enhance MAT by supporting chronic pain management and MMT adherence while preventing drug use and opioid relapse. Results from this study will inform the development of services in New Jersey and other states seeking efficacious strategies to combat the opioid epidemic. If this study demonstrates MORE's efficacy as an adjunct to MMT, we will follow this study with a Stage IV implementation/dissemination study to enhance the rapidity and fidelity of uptake of the intervention into standard of care for persons with OUD.

B. Provide a power analysis. (As applicable, e.g. quantitative research)

We powered the R33 study based on data from prior research. We used a study of an MBI for substance users,⁴ which showed that the hazard ratio of relapse to drug use for the intervention compared to TAU was 0.46. We thus assumed a similar, but more conservative hazard ratio of relapse to opioid use of MORE compared to TAU at about 0.55. (We are using a slightly more conservative hazard ratio than in the original application due to the increased power obtained by reducing the number of treatment conditions from three to two.) We also assumed that the median relapse time to opioid use is 99 days, based on a prior study of relapse to drug use in a general MMT population.⁵ With 1.5 years of subject accrual and an additional follow-up of 16 weeks after the accrual interval, our study needs 47 subjects per group to test a hazard ratio of 0.55 when comparing MORE to TAU, with 80% power and alpha=5% (two-sided). To account for attrition, we will recruit 85 subjects per group (a total of 184 subjects at a 1:1 ratio for MORE vs. TAU).

Version Number: 15, 2/2/2022 Protocol Number: Pro20190016877

PI Name: [name]
Protocol Title: Mindfulness Oriented
Recovery Enhancement (MORE) as an
Adjunct to Methadone Treatment

RESERVED FOR IRB STAMP DO NOT MODIFY THIS SPACE

C. Describe the steps that will be taken secure the data (e.g., training, authorization of access, password protection, encryption, physical controls, certificates of confidentiality, and separation of identifiers and data) during storage, use, and transmission.

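### The 80% power stated for 47 per group assumes independent participants, although MORE is delivered in closed groups of 5 to 9 and the primary analysis adjusts for cohort clustering

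*Combined protocol and SAP*

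**What the plan says.** Section 1.5 states that "our study needs 47 subjects per group to test a hazard ratio of 0.55 when comparing MORE to TAU, with 80% power" at a two-sided alpha of 5%. Section 6.1 B repeats this and adds the event-rate input: "We also assumed that the median relapse time to opioid use is 99 days". Both sections base the calculation on the hazard ratio, accrual and follow-up ("With 1.5 years of subject accrual and an additional follow-up of 16 weeks after the accrual interval"), power and alpha. Neither mentions clustering. Section 1.5 raises the number to 92 per group, 184 in total, and gives attrition as the only reason. Section 6.1 B gives 85 per group beside the same total of 184.

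On delivery, section 1.3 A says of MORE: "Each session will contain 5 to 9 participants". Section 4.3 calls MORE a closed group and randomises participants in blocks within site cohorts of 10 to 18, so each cohort contains both arms.

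On analysis, section 6.1 A, Hypothesis 1.1, says: "Clustering within cohort will be adjusted in the multivariate marginal model analysis". The opening of 6.1 A adds sensitivity analyses for site, group cohort and therapist.

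**The concern.** Members of a MORE group share a therapist and one another's company for eight weekly two-hour sessions, so their outcomes may be correlated. Treatment as usual has no matching study-created group. The analysis plan allows for such correlation, but the power calculation sets it to zero. The test that was powered is therefore not quite the test that will be run.

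If the correlation is positive, the treatment effect is estimated less precisely than assumed, and 47 evaluable participants per group deliver less than 80%. What is at stake is how a null result would be read, and whether the margin between 47 and 92 covers what it needs to cover.

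**Working it through.** **Inputs.** Hazard ratio 0.55, 80% power, two-sided 5%, 47 and 92 per group (1.5); median 99 days, arm not named (6.1 B); accrual 1.5 years = 547.5 days plus 16 weeks = 112 days (1.5); 16 weeks of participation each (1.3 C); MORE group size m = 5 to 9 (1.3 A). The ICC is not in the documents; 0.01 to 0.10 is an assumed range.

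**1. Reproducing 47.** The z-values sum to 1.960 + 0.842 = 2.802, and ln 0.55 = −0.598.
- Schoenfeld events: 4 × 2.802² / 0.598² = 87.8, so 88.
- Freedman events: 2.802² × (1.55/0.45)² = 93.1, rounded up to 94 for equal arms.
- With exponential times and uniform accrual, the event probability is 1 − [exp(−112λ) − exp(−659.5λ)]/(547.5λ).
- If 99 days is the MORE median, the mean event probability is 0.925, and 88/(2 × 0.925) = 47.6 per group.
- If every participant has an event, Freedman gives 94/2 = 47 per group.
- If 99 days is the TAU median, the probabilities are 0.883 (TAU) and 0.729 (MORE). Then 88/(0.883 + 0.729) = 54.6, so 55 per group, and power at 47 is 74%.

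Both routes to about 47 treat participants as independent. No clustering allowance is hidden in the figure.

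**2. Adding clustering.** The design effect 1 + (m − 1) × ICC applies to the MORE arm only. The average variance factor over two equal arms is V = (1 + [1 + (m − 1) × ICC])/2. Taking 47 per group = 80% as given, power at 47 is Φ(2.802/√V − 1.960), and the number that restores 80% is 47 × V.

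Example with m = 7 and ICC 0.05: V = (1 + 1.30)/2 = 1.15. Power = Φ(2.613 − 1.960) = 74.3%. Number needed = 54.05, so 55 per group.

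| Assumed ICC | V (m = 5 to 9) | Power at 47 per group | Per group for 80% | Largest attrition that 92 per group covers |
|---|---|---|---|---|
| 0.01 | 1.02–1.04 | 78.4–79.2% | 48–49 | 47–48% |
| 0.02 | 1.04–1.08 | 76.9–78.4% | 49–51 | 45–47% |
| 0.05 | 1.10–1.20 | 72.5–76.2% | 52–57 | 39–44% |
| 0.10 | 1.20–1.40 | 65.8–72.5% | 57–66 | 28–39% |

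**3. The enrolment margin.** The attrition implied by 1.5 is 1 − 47/92 = 49%. If it occurs, 47 remain and nothing is left for clustering. The only retention figure in the documents is 81% in the pilot trial of chronic pain patients on long-term opioid analgesics (1.4). Applied here, 92 × 0.81 leaves about 75 per group.

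On the protocol's accrual model with 99 days as the TAU median and m = 7, power is Φ(0.598 × √(d/4V) − 1.960), where d is the expected number of events:
- 92 per group, d = 92 × (0.883 + 0.729) = 148: 95% unclustered, 92% at ICC 0.05, 89% at ICC 0.10.
- 75 per group, d = 121: 91%, 87% and 82%. With m = 9 and ICC 0.10 it is 79%.

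**4. Fixed follow-up.** Section 1.3 C says: "Each subject will participate in the study for a total of 16-weeks". Hypothesis 1.1 is analysed at 16 weeks. Event probabilities become 1 − exp(−ln 2 × 112/99) = 0.543 for TAU and 1 − exp(−0.55 × ln 2 × 112/99) = 0.350 for MORE. With 92 per group and no attrition, d is about 82 and unclustered power is 77%. It falls to 70–73% at ICC 0.05 and 63–70% at ICC 0.10. Without clustering, 80% already needs 88/0.894 = 98.5, so 99 per group.

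**The case against.** The strongest reply is that the planned enrolment covers the loss. The protocol attaches 80% to 47 per group and claims no power figure for 92 per group or for 184. A reader might infer that 184 recruited cannot reach 80% because of clustering. The documents do not support that. On the protocol's own accrual model, power stays above 80% over most of the range even at 75 per group (step 3). The shortfall appears there only if attrition uses most of the margin. What remains is that the margin is assigned to attrition alone.

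A reader might also attribute the 77% in step 4 to clustering. It comes entirely from replacing the long follow-up with a fixed 16 weeks, which is a separate problem. Clustering takes off only the further points.

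Third, the correlation may not be confined to MORE. TAU participants share clinics and may attend clinic groups (1.6 A), and both arms share a cohort. Let g be the MORE-group correlation and c the correlation common to both arms of a cohort, with total variance 1 in each arm. For a simple difference in means, the within-cohort contrast has variance g + (1 − c − g)/m + (1 − c)/m. Relative to 2/m, the factor is 1 + (m − 1)g/2 − c. Shared correlation therefore offsets some of the loss, but g is multiplied by 2 to 4 and c only by 1. This supports inflating the MORE arm only. Inflating both arms would overstate the requirement (57–66 rather than 52–57 per group at ICC 0.05). The formula also weights the arms equally although their event probabilities differ, so the figures are approximate.

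Finally, the validity of the test is not in question. The primary model adjusts for cohort, and sensitivity analyses cover site, cohort and therapist. Only the planning figure is affected.

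**Conclusion.** The point stands as an omitted planning assumption. The 80% at 47 evaluable per group belongs to an analysis of independent participants, and no part of the increase to 92 is reserved for clustering. Any net positive MORE-group correlation lowers the stated power: by 1–2 points at ICC 0.01, 4–8 points at 0.05 and about 8–14 points at 0.10. No value in that range can be preferred from the documents, and at 0.01 the loss is negligible.

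These figures take 47 per group = 80% as given, although that holds only on particular readings of the 99-day median. Whether the trial as enrolled falls below 80% depends on attrition and follow-up. It need not under the long follow-up assumed in 1.5. Under fixed 16-week follow-up it does even before clustering, which then adds to the deficit.

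**What to change.** In 1.5 and 6.1 B:
- State an ICC range for MORE groups and its basis.
- Apply 1 + (m − 1) × ICC, with m = 5 to 9, to the MORE arm only.
- State the expected attrition rate separately from the clustering allowance.
- Restate power for the evaluable number expected from 184 recruited, on the follow-up that the primary analysis will actually use.
- Reconcile 85 with 92 per group while editing (2 × 85 = 170, not 184).

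This takes a few lines of calculation. It needs no extra enrolment and no change to conduct or analysis. The only cost is a less favourable stated power.

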1.6 Study Variables

A. Independent Variables, Interventions, or Predictor Variables

Mindfulness Oriented Recovery Enhancement (MORE) structure (Intervention Condition). The MORE arm will participate in eight, weekly, two-hour group sessions led by a therapist on video or phone conference. MORE sessions involve mindfulness training to prevent opioid relapse and reduce pain, cognitive reappraisal to decrease negative affect and regulate opioid craving, and savoring to augment natural reward processing and evoke positive emotion. Each session begins with a mindful breathing or body scan meditation, followed by a debriefing session, in which the therapist provides reinforcement and troubleshooting to help guide successful implementation of mindfulness techniques. Following this debrief of the in-session mindfulness meditation, the therapist debriefs participants' homework practice of using mindfulness, reappraisal, and savoring skills to cope with pain and enhance well-being in everyday life. During this debrief of the homework practice, the therapist provides reinforcement and troubleshooting to help guide successful implementation of mindfulness, reappraisal, and savoring techniques. Next, new psychoeducational material is introduced according to the session topics outlined in Table 3. Sessions culminate with an experiential exercise, and close with a brief mindful breathing meditation. Participants are asked to practice 15 minutes of mindfulness/reappraisal/savoring skills each day (i.e. homework practice).

Table 3. MORE session content								
Week	Theme							
1	Introduction to mindfulness, and the relationship between nociception, pain and emotional suffering; mindful breathing and body scan							
2	Automatic pain coping habits; awareness of automatic opioid use; instruction in mindfulness of automatic pilot; mindful breathing							
3	Mindful reappraisal as means of coping with negative emotions; mindful breathing							
4	Savoring natural rewards; positive emotion regulation; mindful savoring practice							
5	Mindfulness of opioid craving; contemplation of negative consequences of opioid use; imaginal opioid cue-exposure; mindful breathing							
6	The relationship of the stress response to pain and craving; imaginal stress exposure; mindful breathing; body scan							
7	Concepts of thought suppression, aversion, and attachment; exercise in the futility of thought suppression; mindful breathing and acceptance							
8	Discussion of how to maintain mindfulness practice; finding a sense of meaning and purpose of life; development of mindful recovery plan; imaginal rehearsal of skill learning; mindful breathing							

Treatment as Usual (TAU). In the MMT programs, clients typically come to the clinic regularly (usually 6 days per week at the beginning of treatment) to get their methadone dose; during periods of social distancing or as clients progress through the program and remain abstinent from drugs, they can "take home doses" that they can take on days that they are not required to come to the clinic. Timing of the initiation of take-home doses and the scheduling of clinic days varies across clinics. Clients see their clinic substance abuse counselor for individual

7

Version Number: 15, 2/2/2022 Protocol Number: Pro20190016877 PI Name: [name]

Protocol Title: Mindfulness Oriented Recovery Enhancement (MORE) as an Adjunct to Methadone Treatment RESERVED FOR IRB STAMP
DO NOT MODIFY THIS SPACE

counseling, usually weekly at the beginning of treatment, with decreasing frequency if they remain abstinent and progress through treatment. Depending on clients' stage of MMT and success with remaining abstinent from drugs, they may be required to attend clinic treatment groups. During periods of social distancing, these individual or group sessions may be remote, through video conference or phone. Also, some clients may choose to go to voluntary counseling, educational, or support groups (none of these groups involve coping with pain oriented or are mindfulness-based). All individual treatment characteristics, including methadone dosage, take-home dosing, clinic attendance and attendance at clinic counseling sessions and groups (whether in-person or remotely), will be documented for all study participants and entered as covariates in the analyses.

B. Dependent Variables or Outcome Measures

In addition, the study will explore outcomes among participants in the MORE condition relative to treatment as usual (TAU) in regard to opioid use outcomes such as:

- Time until first opioid lapse (primary outcome)
- Opioid abstinence
- Time until MMT dropout
- Total days of methadone treatment
- Total days of opioid or any drug use
- Trajectories of positive and negative affect
- Drug craving
- Pain severity and pain interference

